**1 The drug/biologic/product being administered is an investigational product (not approved by the FDA)**

Generic Name	Type of Product	Manufacturer
There are no items to display		

**2 The drug/biologic/product being administered is an FDA-approved agent but used outside of the FDA labeling in an unapproved dose, route of administration, population, disease, in concomitant medical use, etc.**

Generic Name	Type of Product	Manufacturer
View cabergoline	Drug	Teva Pharmaceuticals

**3 The drug/biologic/product being administered is FDA approved and being administered in accordance with approved labeling**

Generic Name	Type of Product	Manufacturer
View norethindrone acetate	Drug	Amneal Pharmaceuticals

**4 The drugs/biologics/products being administered does not fit into any of the above categories.**

Generic Name	Type of Product	Manufacturer
--------------	-----------------	--------------

There are no items to display

**5 The product being administered is a dietary supplement, herbal medicine, or medical food.**

Product Name	Type Of Product
--------------	-----------------

There are no items to display

## Placebo

**1 \* Briefly describe the placebo (drug, device, procedure, intervention, surgery, etc.) arm used in the study. Provide a justification for use of the placebo, including the length of subject participation in the placebo arm. Please justify why the study cannot be conducted without the use of the placebo. Your justification should address whether outcomes are subjective and how use of a placebo will address this issue, if applicable.**

No subjects in the proposed pilot study will be denied treatment. Subjects will be randomized to either receive norethindrone acetate (standard care) versus cabergoline (investigational drug).

However, since the two medications are administered on a different frequency, a placebo will be used to maintain blinding of drug assignment to both the investigators and the subject.

If a subject is randomized to norethindrone acetate, she will receive norethindrone acetate 5 mg tablet by mouth daily + one placebo pill by mouth twice weekly.

If a subject is randomized to cabergoline, she will receive one placebo pill by mouth daily + cabergoline 0.5 mg tablet by mouth twice weekly.

As a result, all subjects will take 1 pill daily and 1 pill twice weekly. This will allow both the patients and investigators to remain blinded to group assignment.

**2 \* Describe any commonly used diagnostic/treatment approach(es) that will be withheld from subjects assigned to the placebo arm of this study. Will subjects be denied any type of treatment or diagnostics that would be considered a current standard of care?**

No subjects will receive only placebo. All subjects will receive active treatment. All subjects will receive either the intervention medication or the standard of care.

**3 \* Summarize any risks to subjects in the placebo arm consequent to not receiving active treatment for their disease or condition.**

No subjects will receive only placebo. All subjects will receive active treatment.

**4 \* Summarize the potential benefits from participation in this protocol for subjects in the placebo arm.**

No subjects will receive only placebo. All subjects will receive active treatment.

**5 If applicable, how will the condition or disease of subjects in the placebo arm of this study be monitored compared to the monitoring associated with standard care for this disease/condition?**

No subjects will receive only placebo. All subjects will receive active treatment.

**6 If applicable, what criteria will be used to determine that the participation of a subject, who may be receiving a placebo treatment, should be discontinued due to his/her worsening disease or condition?**

No subjects will receive only placebo. All subjects will receive active treatment.

**Title: Novel Treatments for Endometriosis (NOTE): Dopamine Receptor Agonist Therapy for Pain Relief in Women Suffering from Endometriosis Pilot Study**

## Blood Collections

**1 Select the method(s) of blood collection.**

- 1.1  Venipuncture
- 1.1.1  At time of clinically indicated procedure
- 1.1.2  At time specifically for research
- 1.2  Heel/finger/ear sticks
- 1.3  From catheter or heparin lock
- 1.4  Other

*If Other:*

1.4.1 Please specify.

2 \* **How many individual samples will collected (not number of sticks)?**

One sample will be collected per research study visit, for a total of 3 samples over 6 months.

*Note: Multiple withdrawals of blood from an indwelling venous line are to be considered more than one collection.*

3 \* **What is the period of time the samples will be collected (please specify in weeks or if less than weeks in days)?**

Samples will be collected at baseline, 3 months, and 6 months.

4 \* **Specify the total amount of blood collected in mls.**

maximum 40mLs

5 \* **Will research subjects be less than 16.5 kg?**

Yes  No

*If YES:*

5.1 **Will the total amount of blood to be drawn from children less than 16.5 kg be more than 3mL/kg?**

Yes  No

**Title: Novel Treatments for Endometriosis (NOTE): Dopamine Receptor Agonist Therapy for Pain Relief in Women Suffering from Endometriosis Pilot Study**

**Additional Documents**

1 **Please upload any additional documents if it is necessary.**

Name	Date Last Modified	Version	Owner
There are no items to display			

**Detailed Sponsor Information****1 \* What is the sponsor's name?**

J WILLARD AND ALICE S MARRIOTT FOUNDATIO - 1754

**1.1 If your sponsor is not in the list, please select "Other" from the list and specify your sponsor below.***Note: Use a '%' to conduct a wildcard search (e.g. a '%Pharm' search will return all options with 'pharma' at any place in the name).***2 \* Please select the appropriate category of funding.**

- Federal
- State
- Corporate/Industry
- External Foundation**

**2.1 If the category of funding is "Federal", upload the grant(s) here. (Please include the scientific part. This is a requirement for federally supported research. You need not include biosketches or financial information here, just the description of the research.)**

Name	Date Last Modified	Version	Owner
There are no items to display			

**3 \* What will the sponsor provide? Check all that apply:**

Research Funding - Committed

**8 \* Is a Clinical Trial Agreement (CTA) required?**

- Completed/Signed
- Pending
- Not Required**

ID: VIEW46F5DA7D2D400  
Name: Detailed Sponsor Information

**Detailed Sponsor Information****1 \* What is the sponsor's name?**

MARRIOTT DAUGHTERS FOUNDATION - 1822

**1.1 If your sponsor is not in the list, please select "Other" from the list and specify your sponsor below.***Note: Use a '%' to conduct a wildcard search (e.g. a '%Pharm' search will return all options with 'pharma' at any place in the name).*

**2 \* Please select the appropriate category of funding.**

- Federal
- State
- Corporate/Industry
- External Foundation**

**2.1 If the category of funding is "Federal", upload the grant(s) here. (Please include the scientific part. This is a requirement for federally supported research. You need not include biosketches or financial information here, just the description of the research.)**

Name	Date Last Modified	Version	Owner
------	--------------------	---------	-------

There are no items to display

**3 \* What will the sponsor provide? Check all that apply:**

Research Funding - Committed

**8 \* Is a Clinical Trial Agreement (CTA) required?**

- Completed/Signed
- Pending
- Not Required**

ID: VIEW46F5DA7D2D400  
Name: Detailed Sponsor Information

**Use of an Approved Drug/Product for an Unapproved Indication****1 \* Select the type of product that will be administered that is relevant to the aims of the research protocol. If there is more than one product, enter information about one product at this time. You will be able to enter additional products at a later time.**

- Drug**
- Biologic
- Combination
- Other

*If Combination:*

**Please describe. Include whether it is regulated as a drug/device/biologic. What is the mode of action?**

*If Other:*

**Please describe:**

**2 \* What is the generic name or descriptor of the product?**

cabergoline

- 3 **What, if any, is the commercial/trade name of the product?**  
Dostinex
- 4 **\* Who is the manufacturer of the product?**  
Teva Pharmaceuticals
- 5 **\* Who is the supplier of the product?**  
Teva Pharmaceuticals
- 6 **\* Briefly describe how the research use of the product departs from the FDA approved indication/labeling.**  
Cabergoline will be used in the same population of patients as the FDA-approved labeling (reproductive-aged women), but for a different indication (for endometriosis rather than for hyperprolactinemia).
- 7 **\* Describe the purpose of the evaluation (e.g. to support a new indication for the use of the drug, to support any other significant change in the labeling or advertising for the drug, etc.).**  
To determine if cabergoline represents a potential safe and effective means of pain relief for women suffering from chronic pelvic pain related to endometriosis, and to generate preliminary data for a potential larger randomized clinical trial. We do not anticipate this pilot study will lead to any changes in labeling or indication.
- 8 **\* Is this research being conducted under an IND?**  
 Yes  No

If YES:

8.1 **Who holds the IND?**

- A company, organization, NIH, consortium or university.
- Children's Investigator**
- Other

8.2 **Specify the IND number if available (if it is not available, you need to submit an amendment to update this information when obtained).**

132882

8.3 **Specify the name of the IND holder.**

[name]

8.4 **Upload a copy of FDA IND approval correspondence, if available.**

Name	Date Last Modified	Version	Owner
FDA go ahead email 3-13-17.docx	3/17/2017 4:13 PM	0.01	[name]
FDA response to 0000.pdf	3/31/2017 11:34 AM	0.01	[name]
FDA Response.01.09.17.docx	3/17/2017 4:13 PM	0.02	[name]
IND submission 0000.pdf	3/31/2017 11:34 AM	0.01	[name]
IND submission 0001.pdf	3/31/2017 11:34 AM	0.01	[name]

8.5 **Is FDA IND approval pending?**

- Yes  No

If NO:

8.6 **Is this research being conducted under a formal IND exemption request to FDA?**

- Yes  No

If YES:

8.7 **Upload a copy of the FDA letter granting the IND exemption.**

Name	Date Last Modified	Version	Owner
There are no items to display			

If NO:

8.8 **Please confirm each statement or provide a justification for each criteria for IND exemption:**

8.8.1 **The drug product is lawfully marketed in the United States.**

- Yes  No

8.8.2 **The investigation is not intended to be reported to FDA as a well-controlled study in support of a new indication and there is no intent to use it to support any other significant**

**change in the labeling of the drug.**

Yes  No

**8.8.3 In the case of a prescription drug, the investigation is not intended to support a significant change in the advertising for the drug.**

Yes  No

**8.8.4 The investigation does not involve a route of administration, dose, patient population, or other factor that significantly increases the risk (or decreases the acceptability of the risk) associated with the use of the drug product.**

**Please explain how the use outside of the approved labeling does not put participants at increased risk due to participation in the study:**

**8.8.5 The investigation is conducted in compliance with the requirements for review by an IRB and with the requirements for informed consent.**

Yes  No

**8.8.6 The investigation is conducted in compliance with the requirements of 21 CFR 312.7 (i.e. the investigation is not intended to promote or commercialize the drug product).**

Yes  No

**8.8.7 Please provide any additional information if necessary.**

**9 \* What is the dosage, route of administration or application, and frequency and total duration of use of the product?**

cabergoline 0.5 mg by mouth administered twice weekly for 6 months

**10 \* What is the proposed mechanism of action of the product? Include any post-manufacturing modifications to the product expected to affect the proposed mechanism of action.**

Analysis of endometriotic lesions has demonstrated that a prerequisite for their formation and maintenance is the development of an adequate blood supply. The regulation of this "endometriotic vasculature" involves well-established pathways of angiogenesis, including vascular endothelial growth factor (VEGF) acting through the VEGF receptor 2 (VEGFR2).

Cabergoline is a long-acting dopamine receptor agonist with a high affinity for D2 receptors, a Drd2-A. In animal models, Drd2-A inhibit pathologic angiogenesis by inactivating VEGFR2 signaling while maintaining an acceptable safety profile and not interfering with the normal establishment and progression of pregnancy.

In a preliminary study that sought to evaluate the efficacy of Drd2-A in the treatment of peritoneal endometriosis in humans, researchers found that Drd2-A led to tissue degeneration, which was supported by down-regulation of VEGF/VEGFR2, three proangiogenic cytokines (CCL2, RUNX1, and AGGF1) and plasminogen activator inhibitor (PAI) 1, a potent inhibitor of fibrinolysis in the L2 lesions

**11 List any contraindications or potential drug interactions.**

Potential Drug Interactions:

Ergot-alkaloids, macrolide antibiotics, other dopamine agonists (phenothiazines, butyrophenones, thioxanthenes, or metoclopramide)

Contraindications:

- uncontrolled hypertension,
- a history of pulmonary, pericardial and retroperitoneal fibrotic disorders
- a history of cardiac valvulopathy of any valve
- a known hypersensitivity to this drug or any ergot derivatives and to any ingredient in the formulation

**12 Are there any known antidotes? Please describe.**

In cases of overdose, symptoms of overdose would likely be those of over-stimulation of dopamine receptors. These might include nausea, vomiting, gastric complaints, hypotension, or thought/perception disturbances (hallucinations), nasal congestion and syncope.

General supportive measures should be undertaken to remove any unabsorbed drug and maintain blood pressure if necessary. In addition, the administration of dopamine antagonist drug may be advisable.

**13 \* Will subjects, or their insurance providers, be charged for the investigational product?**

Yes  No

## 14 Please upload any additional documents, including the approved drug label or package insert.

Name	Date Last Modified	Version	Owner
Dostinex prescribing information	6/3/2015 12:55 PM	0.01	[name]
Dostinex prescribing information 2	6/3/2015 12:55 PM	0.01	[name]

ID: VIEW470A4FA4F4400

Name: Use of an Approved Drug/Product for an Unapproved Indication

## Drug/Product used under Approved Labeling

- 1 \* Select the type of product that will be administered that is relevant to the aims of the research protocol. If there is more than one product which is relevant to the aims of the protocol, enter information about one product at this time. You will be able to enter additional products at a later time.

- Drug
- Biologic
- Combination
- Other

If Combination:

Please describe. Include whether it is regulated as a drug/device/biologic. What is the mode of action?

If Other:

Please describe:

- 2 \* What is the generic name or descriptor of the product?  
norethindrone acetate
- 3 If any, what is the commercial/trade name of the product?  
Aygestin
- 4 \* Who is the manufacturer of the product?  
Amneal Pharmaceuticals
- 5 \* Who is the supplier of the product?  
Amneal Pharmaceuticals
- 6 \* What is the dosage, route of administration or application, and frequency and total duration of use of the product?  
norethindrone acetate 5 mg by mouth daily for 6 months
- 7 \* Will subjects, or their insurance providers, be charged for the investigational product?  
 Yes  No

## 8 Please upload any additional, pertinent documents.

Name	Date Last Modified	Version	Owner
Aygestin prescribing information	6/3/2015 12:56 PM	0.01	[name]

ID: VIEW470A5B5BA5400

Name: Drug/Product Used Under Approved Labeling

### Statistical Plan

The **primary test of interest** for the trial is a comparison of the mean change in pain score, as measured by the BPI, between groups over time. A linear mixed-effects model will be used to estimate the change over time within each group; the model will include fixed effects for group, time, and the group by time interaction and random effects for subject and time (to account for the correlation among observations from the same subject). Estimates and 95% confidence intervals for group differences at each time point will be created using linear contrasts. This pilot study is not designed to determine statistical superiority or equivalence of norethindrone acetate versus cabergoline; rather, the estimates obtained from the mixed model will be used to plan a future randomized controlled trial. **Secondary endpoints** will be analyzed similarly.

**Sample Size:** As the proposed investigation is a pilot study, the sample size has been chosen to provide estimates for the change over time in each group while minimizing the number of subjects exposed to the study treatments. Assuming that we will have an 80% trial completion rate, we will recruit 7 patients to each arm in order to have 5 completers in each randomization group.

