Study participants will be able to contact one of the study physicians at any time if questions or concerns arise. No confidential information from this study or other data within a patient's medical record may be furnished to anyone unaffiliated with Children's Hospital without written consent, except as required by law or regulatory agencies (e.g., FDA).

All participants will be advised to abstain from sexual intercourse, or to use reliable birth control to prevent pregnancy. A pregnancy test will be performed at each of the 3 study visits.

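### With three visits, can the SAP's mixed model be fitted, and does it leave the group difference at each visit undistorted?

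*SAP*

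**What the plan says.** The primary analysis (SAP, Statistical Plan) is "a comparison of the mean change in pain score, as measured by the BPI, between groups over time". The fixed part of the model is given as "fixed effects for group, time, and the group by time interaction". For the within-subject part, the SAP names "random effects for subject and time (to account for the correlation among observations from the same subject". The output is set out as follows: "Estimates and 95% confidence intervals for group differences at each time point will be created using linear contrasts". The same paragraph says that the pilot is not meant to show superiority or equivalence, and that its estimates will serve to plan a later randomised trial.

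The section does not state how time is coded in the fixed or random part, the covariance structure, the degrees-of-freedom method, or what to do if the model fails to converge.

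The protocol has three visits (Risks and Benefits, item 3: "A pregnancy test will be performed at each of the 3 study visits"). Their timing is given for blood sampling (Blood Collections, item 3): "Samples will be collected at baseline, 3 months, and 6 months". No BPI schedule appears in the documents, so one BPI score per visit is an assumption here. The Protocol and Appendices section lists a separately uploaded study protocol, which is not among the documents reviewed. Its required contents include the assessment schedule and a data analysis plan.

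**The concern.** Three visits give each subject only 3 variances and 3 covariances, 6 quantities in all. If time is a factor in both parts of the model, a random intercept plus two correlated visit effects uses all 6, and the residual makes 7. The model is then not identifiable. A single subject-by-visit variance fails too, because it cannot be told apart from the residual with one score per subject and visit.

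If time is instead a number, the model can be identified, but the fitted group differences at months 0, 3 and 6 must lie on a straight line. That sits badly with a plan to report a difference at each time point.

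Even an identifiable random-slope model is fragile with 10 to 14 subjects. Simulated boundary fits (slope variance at zero, or correlation at plus or minus 1) ran at 58-67% with no true slope variance and at 29-52% with some. Since the estimates are meant for planning the next trial, biased differences or degenerate variance components would be carried forward.

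**Working it through.** **Plan's own figure.** The SAP wants 5 completers per arm: "Assuming that we will have an 80% trial completion rate". 5 / 0.8 = 6.25, rounded up to 7 per arm, 14 in total. This agrees with the SAP and with Subject Information in the protocol.

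**Step 1: which readings can be identified?** For each reading, count the covariance parameters and find how many can be separated from three visits (the rank of the map from parameters to the 6 variances and covariances).

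| Reading of the random part | Parameters | Rank |
|---|---|---|
| Intercept + two correlated visit effects + residual | 7 | 6 |
| Intercept + subject-by-visit + residual | 3 | 2 |
| Intercept + two independent visit effects + residual | 4 | 4 |
| Intercept + linear slope, correlated, + residual | 4 | 4 |
| Intercept only + residual | 2 | 2 |

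The first two fail and the others do not. None of them dictates how time enters the fixed effects. Visit can therefore be a three-level factor in the means, with no straight-line constraint, alongside a random intercept and linear slope.

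**Step 2: what fails when identifiability fails?** With visit as a factor, the fixed part has 2 groups x 3 visits = 6 parameters and rank 6. With complete data, the visit contrasts came out identical under three different covariance matrices, because the model reproduces the group-by-visit means whatever the covariance. With dropout the contrasts do depend on the covariance, but only through the 6 marginal variances and covariances. These remain estimable in the 7-parameter reading; only their split into components is lost.

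**Step 3: the straight-line reading.** Assume true differences 0, 2, 2 at months 0, 3, 6. The mean is 4/3. The slope is [(-3)(0) + (0)(2) + (3)(2)] / (9 + 0 + 9) = 6/18 = 1/3 per month. Fitted values are 4/3 - 1 = 0.33, then 1.33, then 4/3 + 1 = 2.33, so the errors are +0.33, -0.67, +0.33. A true pattern of 0, 0, 2 is fitted as -0.33, 0.67, 1.67. A linear 0, 1, 2 has no error.

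**Step 4: simulation.** 250 trials were run with 7 per arm and 20% dropout. The true difference was 0, -2, -2, and the SDs were assumed (intercept 1.4, slope 0.15 per month, residual 1.2). Fits used REML, with intervals of estimate plus or minus 1.96 SE.

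| Model | Mean estimate, month 3 / 6 | Empirical SD | Coverage | Warnings or failures |
|---|---|---|---|---|
| Visit factor, random intercept + slope | -2.04 / -1.97 | 1.05 / 1.33 | 95% / 94% | 142 of 250 |
| Linear time, random intercept + slope | -1.32 / -2.40 | 0.93 / 1.27 | 86% / 91% | 154 of 250 |
| Visit factor, random intercept only | -2.04 / -1.96 | 1.05 / 1.32 | 94% / 88% | 1 of 250 |

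The Monte Carlo standard error of a 95% coverage figure is sqrt(0.95 x 0.05 / 250) = 1.4 percentage points.

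Root mean squared error puts the bias in proportion. At month 3, linear time gives sqrt(0.68² + 0.93²) = 1.15 and the factor model sqrt(0.04² + 1.05²) = 1.05. At month 6 they are sqrt(0.40² + 1.27²) = 1.33 and sqrt(0.03² + 1.33²) = 1.33.

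**Step 5: would another covariance do better?** A second simulation used the same size, dropout and true difference, again with assumed SDs. Visit as a factor with random intercept and slope gave -2.02 and -1.99, with coverage of 94% and 92% (normal intervals) or 95% and 94% (t intervals). An unstructured 3x3 covariance gave the same means, with 93% and 89% (normal intervals). Linear time gave -1.34 and -2.39.

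**The case for a change.** The best case for a change is that the sound reading is one of several and the SAP does not choose it. That reading produced warnings or failures in 142 of 250 trials, so a fallback would probably be picked after the data are seen. The simplest fallback, a random intercept alone, covered only 88% at month 6. Normal intervals would also run short: if the contrast behaves as a t statistic, nominal 95% intervals cover about 91.4% on 8 degrees of freedom and 92.6% on 12. The secondary endpoints take the same model, and the missing sentences would cost little to write.

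The under-specification is real, and so is the fragility of the variance components; a slope variance or correlation taken from so few subjects is a poor planning input. Neither shows harm to the reported differences. The warnings, whose number depends on the optimiser, left the means unbiased and coverage at 95% and 94%. The random-intercept fallback was unbiased as well, and its shortfall at month 6 depends on the assumed slope variance. Normal intervals are themselves an assumption, since the SAP names no method, and small-sample degrees of freedom are an ordinary choice for an analyst with 14 subjects.

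The obvious substitute, an unstructured covariance, brings no clear gain. It spends 6 parameters where intercept plus slope spends 4, and its coverage was slightly lower. With complete data it reduces the difference in change to the two-sample t interval, but the plan expects dropout.

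**Conclusion.** The concern does not call for a change. It requires that every reading of the model either fails or forces a line, and that is not so. A plan that promises a contrast at each time point points naturally to visit as a factor, and with that coding the estimates are unbiased and coverage is close to nominal. On the non-identifiable readings only the variance split is lost, and dropping the redundant term leaves the mean model as it was.

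Bias arises only if time is fitted as a straight line and the true difference is not linear. In the assumed 0, 2, 2 pattern it reaches 0.67 points at month 3, where root mean squared error rises from 1.05 to 1.15; at month 6 it is 1.33 either way. The documents give no effect size, SD or response shape, so these figures are illustrative.

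What remains is a gap in modelling detail in a pilot of 14 that tests no hypothesis, and an analyst would fill it sensibly. The choice between unstructured and intercept-plus-slope covariance is a matter of preference. The conclusion assumes one BPI score at each of three visits and rests on the simulations' assumed SDs.
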